Date: February 29, 2020

NCT number: Not

Available

Official Project Title

Investigating the Role of Yoga in Alleviating
Chromosomal Translocations in Security Guards
of Chandigarh Police Who Are Responsible for
the Safety of VIPs

Statistical Analysis Plan (SAP)

1. Introduction

This Statistical Analysis Plan (SAP) outlines the planned analyses for the study titled “Investigating the Role of Yoga in Alleviating Chromosomal Translocations in Security Guards of Chandigarh Police Who Are Responsible for the Safety of VIPs”. It defines the methods for analyzing study endpoints, including descriptive, inferential, and correlation analyses.

2. Objectives and Endpoints

1. Analysis of molecular markers related to DNA damage response and repair before and after the practice of yoga on Chandigarh Police.
2. To examine the molecular mechanism by which yoga may modulate DNA damage response and repair.

3. Analysis Populations

- **Full Analysis Set (FAS):** All participants meeting eligibility criteria and providing baseline and outcome data.
- **Per-Protocol Set (PPS):** Subset of participants completing the study without major protocol deviations.

4. General Statistical Considerations

- All analyses will be conducted using **GraphPad Prism v8.0.2** and **JASP v0.19.3**.
- Two-sided significance level of $\alpha = 0.05$ will be applied.

- Adjusted p-values from post hoc tests will also use the **0.05 threshold** for significance.
- Continuous variables will be summarized with **mean \pm SD** (if normally distributed) or **median with interquartile range** (if non-normal).
- Categorical variables will be summarized as **frequencies and percentages**.

5. Assessment of Assumptions

- **Normality:** Assessed using the **Shapiro-Wilk test**.
- **Homogeneity of variance (ANOVA assumption):** Checked using **Levene's test**.

6. Statistical Methods

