### *Exclusion criteria*

- i. Guards with complications in co-morbid conditions like Diabetes, Cirrhosis, etc.
- ii. Guards of age less than 20 or more than 60 years.
- iii. Guards who do not consent to be a part of this study.
- iv. Guards who fail to comply with the yoga protocol in Intervention Group.

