6.1 Comparisons of Two Groups

- **Normally distributed data:** Student's *t*-test (paired or unpaired as appropriate).
- **Non-normal data:** Wilcoxon matched-pairs signed rank test (paired) or Mann-Whitney test (independent).

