6.2 Comparisons of More Than Two Groups

- **Normally distributed data:** One-way ANOVA.
 - **Post hoc:** Dunnett's multiple comparisons test (for comparison against a control group).
- **Non-normal data:** Kruskal-Wallis test.
 - **Post hoc:** Dunn's multiple comparisons test.

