6.3 Correlation Analyses

- **Normally distributed data:** Pearson's correlation coefficient.
- **Non-normal data:** Spearman's rank correlation coefficient.

7. Handling of Missing Data

- Data will be analyzed as observed (complete case analysis).
- No imputation will be performed unless otherwise specified in the protocol.

8. Interim and Sensitivity Analyses

- No interim analyses are planned.
- Sensitivity analyses may be conducted to confirm robustness of results (e.g., excluding participants with protocol deviations).

9. Reporting

- Results will be presented in accordance with **CONSORT/CONSORT-Extension guidelines**.
- Statistical outputs will include effect sizes, 95% confidence intervals, and exact p-values.

Principal Investigator

[name]

Additional Professor

Department of Experimental Medicine and Biotechnology

PGIMER, Chandigarh

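### SAP 5 tests for equal variances but nothing follows from the result; Welch's t-test should replace Student's unpaired t-test as the default

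*SAP*

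**What the plan says.** SAP 5 lists two assumption checks. Normality is assessed by Shapiro-Wilk. Homogeneity of variance, which the SAP labels an assumption of ANOVA, is "Checked using Levene's test". SAP 6 attaches a consequence to the first check only: a marker that fails normality moves to a rank test. A marker that fails the second check moves nowhere.

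For normally distributed data SAP 6.1 names "Student's *t*-test (paired or unpaired as appropriate"). SAP 6.2 names one-way ANOVA followed by "Dunnett's multiple comparisons test (for comparison against a control group"). Neither document names an unequal-variance test, a robust standard error or a transformation. The sensitivity analyses in SAP 8 are optional, and their one example is leaving out participants with protocol deviations.

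Three other places bear on the final arm sizes:
- Item iv of the protocol's exclusion criteria removes "Guards who fail to comply with the yoga protocol in Intervention Group".
- SAP 3 limits the Full Analysis Set to participants who meet the eligibility criteria and have baseline and outcome data.
- SAP 7 specifies complete-case analysis.

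SAP 9 commits to the quantities at issue: "Statistical outputs will include effect sizes, 95% confidence intervals, and exact p-values".

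**The concern.** Student's unpaired t-test estimates a single variance from both arms. When the arms differ in size and in spread, the larger arm dominates that estimate and the standard error of the difference is biased. If the smaller arm is the more variable one, the standard error is too small: the test rejects too often and the interval is too narrow. If the smaller arm is the less variable one, the test is conservative and power is lost.

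The exclusion for non-compliance can shrink only the yoga arm, so the plan itself offers a route to unequal arms. Levene's test as written would not protect the two-arm comparison, because it is tied to ANOVA and decides nothing. A significant result would leave the analyst to choose a method after seeing the data. The point is separate from the normality check, since it concerns markers that pass Shapiro-Wilk.

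**Working it through.** **Inputs from the documents.** Two-sided level 0.05 (SAP 4). 206 participants needed and 229 recruited to allow for 10% dropout (protocol, Methodology). The dropout step reproduces: 206 / 0.9 = 228.9, rounded up to 229.

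**Assumptions, because the documents give no figure.** 1:1 allocation (114 and 115 recruited); normal outcomes; ratio r of yoga SD to control SD between 0.5 and 2, with control SD = 1; and these final arm sizes (yoga v control):
- 103 v 103: the 206 split equally.
- 92 v 114: again 206 in total, with nearly all the planned loss in the yoga arm.
- 72 v 103 and 60 v 103: heavy one-sided loss. From about 114, these are losses of 37% and 47% in yoga, against 10% in control.

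**Approximation.** With n1 in yoga and n2 in control:
- true variance of the mean difference: V = r²/n1 + 1/n2
- variance the pooled test uses, on average: P = [((n1−1)r² + (n2−1)) / (n1+n2−2)] × (1/n1 + 1/n2)
- type I error ≈ 2 × [1 − Φ(t × √(P/V))], where t is the two-sided 5% critical value

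At 72 v 103 with r = 2:
- V = 4/72 + 1/103 = 0.0653
- P = (71×4 + 102)/173 × (1/72 + 1/103) = 2.231 × 0.0236 = 0.0527
- √(P/V) = 0.898 and t = 1.974, so type I error ≈ 7.6%

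At 72 v 103 with r = 0.5:
- V = 0.25/72 + 1/103 = 0.0132
- P = (71×0.25 + 102)/173 × 0.0236 = 0.692 × 0.0236 = 0.0163
- √(P/V) = 1.113, so type I error ≈ 2.8%

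With equal arms of size n, P = (r² + 1)/n = V. The bias vanishes whatever the SD ratio.

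**Simulation.** The approximation ignores sampling error in the variances, so the exact behaviour was simulated (4,000,000 trials per cell). Type I error of Student's t at nominal 5%:

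| Yoga v control | r = 0.5 | r = 1.5 | r = 2 |
|---|---|---|---|
| 103 v 103 | 5.0% | 5.0% | 5.0% |
| 92 v 114 | 3.7% | 6.0% | 6.7% |
| 72 v 103 | 3.0% | 6.7% | 7.9% |
| 60 v 103 | 2.2% | 7.7% | 9.6% |

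Interval coverage is 100% minus each entry: at 92 v 114 it runs from 96.3% down to 93.3%. Welch's t-test was at 5.0% in every cell.

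**Power.** At 72 v 103, r = 0.67 and a true difference of 0.35 control SD, power is 74.5% with Student and 78.7% with Welch. With equal variances and the same difference, Welch loses about 0.07 percentage points at 72 v 103 and about 0.15 at 60 v 103, so no more than about 0.2.

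**ANOVA and Dunnett.** Here equal group sizes do not remove the problem. With four independent groups of 103 (an assumed layout) and one SD doubled, the type I error of one-way ANOVA is 6.5%. Dunnett's error is then spread unevenly: about 0.2% for a contrast with an unchanged group against 4.9% for the group whose SD changed. With one SD halved instead, Dunnett's familywise error is 6.8%.

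**The case against.** The strongest reply is that the harm needs two conditions together and the documents establish neither. No SDs are given, and nothing shows that yoga changes the spread of any marker; a mixed response to the programme is conjecture. Item iv makes one-sided removal possible but does not show how much will occur. At the planned 10% dropout, even with nearly all of it in the yoga arm, the error moves by only about 1 to 1.7 percentage points, and that at SD ratios of 1.5 to 2 or of 0.5. The figures near 8% to 10% need more than a third, or about half, of the yoga arm to be lost. All of this stands, and it limits the weight of the point.

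The reach is also narrow. The first objective is a before-after analysis, and a paired t-test does not pool arm variances. Markers that fail Shapiro-Wilk go to rank tests, which this point does not address. Only unpaired comparisons of normally distributed markers are affected.

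A reader might also infer unequal arms from the lack of a stated allocation ratio. That does not hold: the protocol has a flow chart on allocation of the sample size whose content is not shown in the text available, and the ratio may be there.

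Finally, one could keep Levene's test and state what follows from it. That would close the gap, but a default Welch test is simpler and needs no data-driven choice.

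**Conclusion.** The gap in the plan is certain: the variance check has no consequence, and the tests named for independent groups with normally distributed data all pool the variance. The effect on results is conditional. If the arms end unequal in both size and spread, type I error of the unpaired t-test could lie anywhere from about 3.7% to 6.7% at the planned level of loss, and from about 2.2% to 9.6% under heavy loss confined mainly to the yoga arm. These ranges rest on assumed 1:1 allocation, SD ratios of 0.5 to 2 and assumed final arm sizes.

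A reader might go further and conclude that the yoga-versus-control test fails its 5% level as planned. The documents do not support that: with equal arms, or with equal spread, Student's t is sound. It would equally be wrong to say that unequal arms are always needed, since ANOVA and Dunnett can be distorted with equal groups. The point is minor, and worth acting on because the remedy costs almost nothing.

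**What to change.** In SAP 6.1, make Welch's t-test the default for every independent two-arm comparison of normally distributed data, not conditional on Levene's test. Keep the paired t-test for within-person change. In SAP 5, remove Levene's test or mark it as descriptive only.

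If SAP 6.2 is used for independent groups, replace one-way ANOVA and Dunnett with Welch's ANOVA followed by an unequal-variance comparison of each group against control, for example Welch t-tests against control with Holm adjustment. An all-pairs procedure such as Dunnett T3 would not match the comparison that SAP 6.2 asks for. This replacement does not suit arm-by-time cells: the trial has two arms, so such cells contain repeated measures on the same people, and Welch's ANOVA does not handle those.

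The cost is a few words in SAP 5, 6.1 and 6.2, with no extra data and at most about 0.2 percentage points of power for the two-arm test when variances are equal.

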6.1 Comparisons of Two Groups

- **Normally distributed data:** Student's *t*-test (paired or unpaired as appropriate).
- **Non-normal data:** Wilcoxon matched-pairs signed rank test (paired) or Mann-Whitney test (independent).

6.2 Comparisons of More Than Two Groups

- **Normally distributed data:** One-way ANOVA.
 - **Post hoc:** Dunnett's multiple comparisons test (for comparison against a control group).
- **Non-normal data:** Kruskal-Wallis test.
 - **Post hoc:** Dunn's multiple comparisons test.

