### Methodology

Recruitment of individuals: Department of Police, Chandigarh has agreed to help us on this aspect. Policemen working for Chandigarh Police will be chosen based on the inclusion and exclusion criteria.

Subjects: Those security guards (age: >20 and <60) who are willing to consent to participate in this study will be screened for moderate and higher stress on Cohen's PSS, according to inclusion criteria and randomly divided between Intervention (Yoga Group) and Control Group.

Sample Size: The sample size of 206 was calculated for 99% confidence level (reliability coefficient = 2.58), at the alpha level of 0.05, a power of 0.95, and a relative precision of 0.2, derived from a pilot study done on breast cancer patients and yoga practitioners (Ram et al, 2013). Assuming a 10% drop out rate, a total of 229 subjects will be recruited.

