### **Design of the study**

In a randomized control trial (RCT), participants are allocated randomly between intervention and control groups to compare the treatments, which enables statistical control over the influences imparted by the aforementioned treatments. In the present study, the policemen who satisfy our eligibility criteria and willing to consent to participate in our study will be enrolled, grouped randomly in intervention and control groups, and assessed for the dependent variables of the study before and after the Integrated Yoga intervention period.

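### The SAP names no between-arm analysis that uses the day-0 value, and section 6.2 does not say which groups its independent-group tests compare

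*SAP*

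**What the plan says.** The protocol describes two arms. Under Methodology, guards are "randomly divided between Intervention (Yoga Group) and Control Group"; under Design of the study they are "assessed for the dependent variables of the study before and after the Integrated Yoga intervention period". The timetable under Variables lists cortisol, immunofluorescence, gene expression, translocation PCR and the comet assay at day 0 and again at 3 months. Key question (b) of the protocol asks about a change in DNA repair capacity relative to matched controls.

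SAP 6.1 gives a t-test, "paired or unpaired as appropriate", with the Wilcoxon signed rank or Mann-Whitney test for non-normal data. SAP 6.2, for more than two groups, gives one-way ANOVA followed by "Dunnett's multiple comparisons test (for comparison against a control group", or the "Kruskal-Wallis test" followed by "Dunn's multiple comparisons test". It does not identify the groups. The SAP mentions no analysis of covariance, change score, mixed model, repeated-measures ANOVA, Friedman test or arm-by-visit term.

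**The concern.** In a two-arm trial with a baseline and one follow-up visit, the question is whether the arms differ at 3 months given where they started. The SAP leaves the analyst to decide which pairs of data 6.1 compares and whether the day-0 value is used at all.

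Section 6.2 adds to the uncertainty. Two arms and two visits give four cells, and these are the only set of more than two groups, control included, that the text defines for the guards' pre/post data. One-way ANOVA, Kruskal-Wallis, Dunnett and Dunn all assume independent groups, whereas the four cells contain each guard twice. No single contrast against one reference cell is the between-arm difference in change, and the SAP does not fix the reference cell. At stake are power that the collected baseline data would provide at no cost and, under one possible use of 6.2, a change common to both arms being reported as a yoga effect.

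**Working it through.** **Inputs from the documents.** Two arms and two visits (protocol, Methodology and Design of the study). 206 evaluable guards and 10% dropout (protocol, Sample Size). "Two-sided significance level of $\alpha = 0.05$ will be applied" (SAP section 4).

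**The plan's own figure.** 206 / (1 − 0.10) = 228.9, rounded up to 229, which matches the protocol. This point changes no sample-size figure.

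**Assumptions not in the documents.** 1:1 allocation, so 206 / 2 = 103 per arm; normal data with SD 1 at both visits; visit correlation ρ of 0.3, 0.5 or 0.7; a true yoga effect of 0.35 SD, or a shift of 0.3 SD common to both arms. The two-sided Dunnett critical value for three comparisons, found by simulation, is about 2.35.

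**Step 1: standard error of a between-arm difference at one visit.** √(2/103) = 0.1393.

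**Step 2: power of yoga versus control at 3 months, effect 0.35 SD.** The standardised effect is 0.35 / 0.1393 = 2.51. Power is approximately Φ(standardised effect − critical value).

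| Analysis | Standardised effect | Critical value | Power |
|---|---|---|---|
| Unpaired t-test at 3 months | 2.51 | 1.96 | 71% |
| Same contrast within Dunnett | 2.51 | 2.35 | 56% |
| Baseline-adjusted, ρ = 0.3 | 2.51/√(1 − 0.09) = 2.63 | 1.96 | 75% |
| Baseline-adjusted, ρ = 0.5 | 2.51/√(1 − 0.25) = 2.90 | 1.96 | 83% |
| Baseline-adjusted, ρ = 0.7 | 2.51/√(1 − 0.49) = 3.52 | 1.96 | 94% |

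Simulation agrees: about 70-71% for the t-test, 56% for Dunnett, and 74%/83%/94% with baseline adjustment. About 14 to 15 points of the gap between Dunnett and the adjusted model are therefore Dunnett's multiplicity penalty. The gain from using the baseline is the rest: about 4, 12 and 23 points.

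**Step 3: unpaired test on change scores, effect 0.35 SD.** This is one possible reading of 6.1. The standardised effect is 2.51/√(2(1 − ρ)) = 2.12, 2.51 and 3.24, giving power of 56%, 71% and 90%. It is never better than the baseline-adjusted model here, and at ρ = 0.3 it is worse than ignoring the baseline.

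**Step 4: 6.2 on the four cells, no yoga effect, both arms shift by 0.3 SD.** For yoga at 3 months against control at day 0, the standardised difference is 0.3 / 0.1393 = 2.15. The rejection rate is Φ(2.15 − 2.35) = Φ(−0.20), about 42%. Simulation gives about 41-42%, hardly affected by ρ because the two cells hold different guards. The baseline-adjusted comparison stays near 5%.

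**Step 5: ignoring the pairing.** Treating a guard's two values as independent inflates the standard error of a within-arm change by 1/√(1 − ρ) = 1.20, 1.41 and 1.83. With a control cell as the Dunnett reference, only one of the three contrasts is within guards: control 3 months against control day 0. With nothing changing, its rejection rate is 2(1 − Φ(2.35/√(1 − ρ))), about 0.5%, 0.09% and 0.002%, against about 2% for independent values. The error is conservative.

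**The case against.** The strongest reply is that the SAP never says 6.2 will be applied to arm-by-visit cells. The protocol's Novelty section mentions cell-line work alongside human subjects, and the second objective is mechanistic. Several culture conditions against an untreated control would be a proper use of one-way ANOVA with Dunnett. Diet or alcohol categories could also form independent subgroups. The work-plan figure is not available in the text. Section 6.1 already separates paired from independent data, and the two-arm and before-after comparisons fit there. All of this stands. A reader might infer that 6.2 is the planned analysis of the trial and that its results will be wrong; the documents do not support that.

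A reader might also infer that every contrast in 6.2 would be invalid. That too goes too far. Yoga against control at 3 months is a randomised comparison and estimates the same effect as the difference in change. Ignoring the baseline there costs precision, not validity. The false positives in step 4 require both a common shift over time and a choice of control day 0 as reference despite a concurrent control.

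What the objection leaves untouched is that 6.1 does not say whether its unpaired tests apply to 3-month values or to changes, and no baseline-adjusted method is named for the guards' data.

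**Conclusion.** The point holds as under-specification with a free improvement available. The SAP names no between-arm analysis that uses the day-0 value and does not say what 6.2 compares.

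Under the stated assumptions, baseline adjustment raises power from about 70-71% to about 74%, 83% or 94% as the visit correlation goes from 0.3 to 0.7. The benefit is small if the markers are weakly correlated between visits and large if they are strongly correlated; the documents give no correlation. The 41-42% false-positive rate is conditional on 6.2 being applied to the four cells with control day 0 as reference and on a 0.3 SD shift in both arms. It shows why that use should be ruled out in writing and is not a forecast of what this trial will do.

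**What to change.** In the SAP, for each continuous marker measured in the guards at both visits, make the main analysis one baseline-adjusted model. This can be the 3-month value regressed on arm and the day-0 value, with a transformation if the marker is skewed, or a mixed model for repeated values within guard with an arm-by-visit term. Report the single between-arm difference with its 95% CI, which fits the reporting commitment in SAP section 9. Keep the paired tests in 6.1 as descriptive within-arm summaries.

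Restrict 6.2 to groups that are truly independent, such as cell-line conditions. Name those groups and the reference, and state that arm-by-visit cells are excluded.

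The cost is SAP wording only. The day-0 values are already planned, so no new data, visits or participants are needed. If the software is kept, confirm that it fits the chosen model.

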6.3 Correlation Analyses

- **Normally distributed data:** Pearson's correlation coefficient.
- **Non-normal data:** Spearman's rank correlation coefficient.

7. Handling of Missing Data

- Data will be analyzed as observed (complete case analysis).
- No imputation will be performed unless otherwise specified in the protocol.

8. Interim and Sensitivity Analyses

- No interim analyses are planned.
- Sensitivity analyses may be conducted to confirm robustness of results (e.g., excluding participants with protocol deviations).

9. Reporting

- Results will be presented in accordance with **CONSORT/CONSORT-Extension guidelines**.
- Statistical outputs will include effect sizes, 95% confidence intervals, and exact p-values.

Principal Investigator

[name]

Additional Professor

Department of Experimental Medicine and Biotechnology

PGIMER, Chandigarh

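### The Full Analysis Set can lose yoga non-compliers and every guard without outcome data, and no planned analysis tests whether the missing guards did worse

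*SAP*

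**What the plan says.** Four rules bear on who is analysed.

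- SAP section 3 defines the FAS as "All participants meeting eligibility criteria and providing baseline and outcome data". The Per-Protocol Set is a smaller group without major deviations.
- SAP section 7: "Data will be analyzed as observed (complete case analysis". Imputation is ruled out unless the protocol specifies it, and the protocol text specifies none.
- SAP section 8: "Sensitivity analyses may be conducted to confirm robustness of results (e.g., excluding participants with protocol deviations". This is permission, not a commitment, and it is the only example given.
- Protocol, Exclusion criteria, item iv: "Guards who fail to comply with the yoga protocol in Intervention Group". This can take effect only after allocation, and only in one arm.

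On numbers, the protocol's sample size paragraph sets a target of 206 and then says: "Assuming a 10% drop out rate, a total of 229 subjects will be recruited".

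**The concern.** The protocol's design section rests the comparison on random allocation. That protection holds for the groups as randomised, not for those who remain after later selection.

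The FAS requires guards to meet the eligibility criteria, and yoga non-compliance is written as one of those criteria. Taken literally, non-compliers leave the main analysis set, not just the per-protocol set. Guards with no 3-month data leave it too.

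The module runs 13 weeks at 5 days a week, in guards whom the protocol describes as on constant alert, and the protocol plans follow-up to secure compliance. Uneven loss is therefore a realistic possibility. If the guards who stop yoga would have had worse 3-month values, the analysis compares selected yoga participants with controls selected differently or not at all. A difference could then appear with no effect of yoga. Removing protocol deviators as well cannot show how the result depends on the guards who are absent.

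**Working it through.** **1. The plan's own figure.** Inputs from the protocol's sample size paragraph: 206 evaluable, 10% drop-out, 229 recruited.

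- 206 / (1 - 0.10) = 228.9, rounded up to 229. The stated figure is reproduced.
- 229 x 0.90 = 206.1. A complete-case analysis keeps 206 at the planned loss.

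There is no slack beyond that. Total loss of 15%, 20% or 30% leaves 229 x 0.85 = 194.7, 229 x 0.80 = 183.2 or 229 x 0.70 = 160.3. The allowance is described as drop-out only; criterion iv removals and missing samples are not budgeted for separately.

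**2. Criterion iv removals on top of drop-out.** Assume 1:1 allocation (114.5 per arm; the ratio is not in the readable text), 10% drop-out in each arm (103.05 left per arm), and a further share q of the remaining yoga guards removed. Analysed total = 103.05 x (1 - q) + 103.05.

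The documents give no effect size. For power, take the difference that 103 per arm detects with 95% power at two-sided 0.05: (1.960 + 1.645) x sqrt(2/103) = 0.502 SD.

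| q (assumed) | Analysed | Power |
|---|---|---|
| 0% | 206.1 | 95.0% |
| 10% | 195.8 | 93.9% |
| 20% | 185.5 | 92.5% |
| 30% | 175.2 | 90.5% |

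The loss of power is modest. Bias is the larger issue.

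**3. Bias from uneven loss.** Suppose leavers are k SD worse than completers on the analysed outcome. An arm that loses a fraction m then has an observed mean too favourable by m x k. The bias in the comparison is (m_yoga - m_control) x k. With no true effect and known SD:

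- SE = sqrt(1/n_yoga + 1/n_control), where n = 114.5 x (1 - m)
- r = bias / SE
- Type I error = P(Z > 1.96 - r) + P(Z < -1.96 - r)

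The test is two-sided at 0.05, as in SAP section 4.

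| Loss, yoga v control (assumed) | n | SE | k (assumed) | Bias (SD) | r | Type I error |
|---|---|---|---|---|---|---|
| 15% v 5% | 97.3 v 108.8 | 0.1395 | 0.5 | 0.10 x 0.5 = 0.05 | 0.358 | 6.5% |
| 15% v 5% | 97.3 v 108.8 | 0.1395 | 1.0 | 0.10 x 1.0 = 0.10 | 0.717 | 11.1% |
| 20% v 0% | 91.6 v 114.5 | 0.1402 | 0.5 | 0.20 x 0.5 = 0.10 | 0.713 | 11.0% |
| 20% v 0% | 91.6 v 114.5 | 0.1402 | 1.0 | 0.20 x 1.0 = 0.20 | 1.427 | 29.7% |

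Both splits lose 10% overall and leave 206.1 guards. The bias can therefore arise with the planned number fully met, and recruiting more guards would not remove it.

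**The case against.** **The sample size is protected.** A reader might infer that the plan fails to keep 206. The documents do not support that: the inflation to 229 is correct and yields 206 at the stated loss. A shortfall needs total loss above 10%, and no non-compliance rate is given. Non-compliers may also overlap with drop-outs, which step 2 ignores.

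**The FAS rule and complete-case analysis are nearly one rule.** With a single post-baseline time point, section 7 mostly restates section 3. This is right; they should not be counted as separate steps away from the randomised groups. Nor does it follow that the section 8 example would confirm a biased result. Removing deviators could enlarge, shrink or leave the difference. The defect is that it does not address the question.

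**The rates and direction are assumed.** This also stands. Controls may leave too, and nothing shows that they would be nearly complete; 20% v 0% is an extreme split. If leavers differ mainly at baseline, analysing change, which the paired tests in SAP section 6.1 would allow, cancels part of the gap. The calculation applies the whole gap to the analysed outcome.

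**CONSORT reporting is promised in SAP section 9.** It should make losses visible by arm. It does not correct or test the bias they may cause.

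**Criterion iv is an intention-to-treat defect, not a missing-data one.** It would remain under any missing-data method and needs its own correction. It belongs here because the FAS definition brings it into the main analysis.

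**Conclusion.** The concern holds in this form: the main analysis set is not the randomised set, one of its filters applies to the yoga arm alone, and no planned analysis asks what happens if guards without outcome data did worse.

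The wording of the rules is established from the documents. The size of the harm is not. Bias of 0.05 to 0.20 SD and type I error of about 6.5% to 30% rest on 1:1 allocation, the two assumed loss splits, and leavers 0.5 to 1.0 SD worse on the analysed outcome. Equal loss with equal gaps in both arms would give no bias under the same formula. The sample size part is conditional: 206 is kept only while drop-out, yoga-arm removals and missing samples together stay within 10%.

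The change should be made, since the flaw lies in stated rules and is cheap to correct.

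**What to change.** - **SAP section 3 and protocol exclusion criterion iv:** define the FAS as all randomised guards analysed by allocated arm. Keep non-compliers in it and measure them at 3 months. Use non-compliance only to define the Per-Protocol Set.
- **SAP sections 6 and 7:** compare arms at 3 months with adjustment for the day-0 value. Multiple imputation from the day-0 value, age and PSS score may support this. It need not be the main analysis, because it relies on the same missing-at-random assumption as a complete-case model adjusted for those variables.
- **SAP section 8:** commit to one delta-adjusted (tipping-point) analysis on a named continuous endpoint with its unfavourable direction stated, for example shifting imputed yoga-arm values by 0.25, 0.5 and 1.0 SD, and report where the conclusion changes. The endpoint must be named because the SAP designates no primary one. An SD shift does not suit translocations if they are scored present or absent, and the documents give no favourable direction for the repair genes.
- **Reporting:** give losses by arm with reasons, separating drop-out, non-compliance and missing samples.

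The cost is SAP and protocol wording, the effort of following non-compliers to 3 months, and some extra analysis, possibly in software beyond the two packages named. Baseline values, age and PSS are already collected. The result may be less favourable to yoga.
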